4. AIMS AND ENDPOINTS

Aim 1. Examine the effects of CAA on alcohol outcomes. Our primary hypothesis is that, relative to AO control, the CAA intervention will (a) increase positive moderate drinking attitudes, (b) decrease positive heavy drinking attitudes, (c) increase attitude-behavior dissonance, and (d) decrease drinks per drinking day, binge frequency, peak BAC, and alcohol consequences, and increase the use of PBS.

Aim 2. Compare the effects of CAA vs. PNF. A secondary hypothesis is that CAA will be no less efficacious than (i.e., not inferior to) PNF in reducing alcohol outcomes as measured by alcohol consumption and alcohol related consequences.

Aim 3. Test specific theory-based mediational pathways. Aim 3a. We predict that the effects of the CAA intervention on alcohol consumption and consequences will be mediated by increases in (a) positive attitudes towards moderate drinking and (b) dissonance (but not perceived norms). Aim 3b. We predict that the effects of the PNF intervention on alcohol

consumption and consequences will be mediated by decreases in (a) perceived descriptive norms and (b) dissonance (but not attitude change).

Aim 4. Test intervention-specific moderators of outcome. Aim 4a. We predict that the effect of the CAA intervention will be enhanced by stronger drinker identity, greater need for consistency, and will not differ by study site. Aim 4b. We predict that response to the PNF condition will be enhanced by weaker drinker identity, greater need for consistency, and will be stronger within a lighter drinking community (the Houston site).

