5. STUDY DESIGN

We will use a multi-site randomized controlled trial (RCT) to evaluate the effects of counter attitudinal advocacy (CAA) relative to assessment only (AO) control on drinking and related problems among college students, and the relative effects of CAA vs. PNF on relevant drinking outcomes. Eligible students will be randomly assigned to one of 3 conditions (personalized CAA or PNF or AO control). Hypothesized mechanisms of change (alcohol-related attitudes and dissonance, perceived drinking norms) will be evaluated immediately after the intervention (posttest) and drinking outcomes (drinks per week, heavy drinking frequency, peak BAC, alcohol-related problems, PBS) will be evaluated at 1-, 3-, and 6-months post-intervention. All procedures are conducted for the purpose of research only.

We propose to conduct this study at two sites (both Carnegie Tier 1 Research universities) that have distinctly different campus and student profiles in order to explicitly test hypotheses about the differential efficacy of CAA vs PNF in different campus contexts. Brown University is a private residential 4-year college with approximately 6200 undergraduates (51% female and 43% minority) and characteristics associated with higher risk of alcohol misuse (e.g., Northeast region, Greek system, athletic tradition). All first- and second-year students and most third-year students live together in on-campus dorms. Students at Brown report high rates of drinking: 81% of Brown students drank in the past 3 months, and 51% report binge drinking in the last two weeks. In contrast, the University of Houston (UH) is a large public research university serving more than 34,716 undergraduate students (51% female and 74% minority). Roughly 80% of UH students live off campus. Located in America's fourth-largest city, UH was designated as the most ethnically diverse metropolitan research university in the United States by Forbes in 2010. UH students report a below average drinker profile, with 45% of the students reporting current drinking and 23% report binge drinking in the last month. Overall, the base rates for any drinking and binge drinking are lower at UH than at Brown. These two sites allow us to test the comparative efficacy of CAA vs PNF in contexts with both high and low base rates of heavy drinking. If site does not moderate efficacy, then the replication of the effects of CAA across sites will provide evidence of generalizability of observed effects.

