6. STUDY POPULATION

6.1. Target Sample. The target sample for analyses is $N=600$ college student drinkers: 300 from Brown University, and 300 from the University of Houston. We will randomize 100 eligible students from each site to the CAA ($n=200$), PNF ($n=200$), and AO ($n=200$) conditions.

6.2. Inclusion Criteria. Inclusion criteria are:

(1) **Age 18-26.** The age range of 18-26 (a) coincides with the distinct developmental period of “emerging adulthood” (Arnett, 2005), (b) is characterized by a high prevalence of heavy episodic drinking (Johnson et al., 2012), and (c) is representative of college students, the majority of whom are 26 years of age or younger (Digest of Education Statistics: 2012).

(2) Male or female student at Brown University or University of Houston. The present study represents a first step in using counter-attitudinal advocacy activities in an attempt to reduce risky drinking behavior. As such, we focus on college students because they exhibit high rates of heavy episodic drinking (Johnson et al., 2012), and their identification with other college peers facilitates the testing of the enhanced manipulation. We recruit at 2 sites that differ in drinking patterns and demographics and geographic location to evaluate the generalizability of the study findings. The findings could have implications for alcohol abuse prevention both with college students and young adults more broadly.

(3) Past month heavy episodic drinking (for men, ≥ 5 drinks in one day, for women ≥ 4 drinks in one day). The 4/5 drink cutoff has been widely used as an indicator of risk ([name], Larimer, & Lewis, 2004; Wechsler & Nelson, 2001) and as a screening criterion in intervention studies targeting heavy drinking students. Our preliminary studies show that heavy drinking frequency is significantly correlated with attitudes towards moderate ($r = -.42$) and heavy ($r = .45$) drinking. By including only drinkers who have reported heavy episodic drinking we optimize the likelihood that developing arguments in favor of moderate drinking ($<4/5$ drinks/occasion) will constitute counter-attitudinal advocacy, and create dissonance between the espoused attitude in favor of moderation and recent behavior.

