10. STATISTICAL CONSIDERATIONS

10.1. Sample Size. Power analyses focus on estimating a sample size large enough to detect “true” effects, thereby avoiding Type II errors. Sample size estimates were obtained for intervention contrasts. Necessary sample sizes were assessed via sample size and power equations for multi-level models using the Optimal Design software program. Based on previous findings using CAA and PNF approaches, we anticipate intervention effects relative to the neutral control condition to be in the small to medium range but at least comparable to effects which have been reported for personalized normative feedback, which are typically in the .28 range (e.g., Dotson et al., 2015). Based on the proposed sample size of 600, given four assessment points, we anticipate the ability to detect effects of intervention contrasts and moderation effects across the small to medium range. Considering maximum anticipated attrition rates of 15% (N=510) we will have .70, .80, and .90 power to detect effects sizes of $\delta = .24, .27, \text{ and } .32$, respectively.

10.2. Analysis Plan. Aims will be evaluated using generalized linear mixed models, an extension of general linear models allowing for multi-level data with non-normal distributions (e.g. Atkins, Baldwin, Zheng, Gallop, & [name], 2013; Hedeker & Gibbons, 2006). With respect to evaluating main effects of experimental conditions on drinking, each participant will provide up to four assessments (baseline, 1-month, 3-month, and 6-month follow-up data). Hypotheses will be tested using specific contrast vectors, using a general linear hypothesis framework (Fox, 2008).

Hypotheses associated with Aim 1 will be evaluated examining outcomes as a function of two dummy coded variables representing CAA and PNF with control as the reference group. Time X CAA outcomes will provide direct tests of differences in change between CAA and control groups. We will utilize a Bonferroni correction with Šídák adjustment for correlated outcomes to reduce alpha inflation associated with multiple outcomes (i.e., moderation attitudes, heavy drinking attitudes, dissonance, drinks per drinking day, binge frequency, peak BAC, alcohol consequences, and PBS use).

For these analyses, each participant will provide up to 4 repeated measures (i.e., baseline, 1-month, 3- months, 6-months), yielding up to 2400 Level 1 cases (repeated-measures) across 600 Level 2

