13. Provide the analysis plan including the power calculation(s). There should be discussion of any planned interim and/or futility analyses, including adjustments for allocating “alpha” on “multiple looks” at the data.

Sample size and power calculations. Power analyses focus on estimating a sample size large enough to detect “true” effects, thereby avoiding Type II errors. Sample size estimates were obtained for intervention contrasts. Necessary sample sizes were assessed via sample size and power equations for multi-level models using the Optimal Design software program.

Based on previous findings using CAA and PNF approaches, we anticipate intervention effects relative to the neutral control condition to be in the small to medium range but at least comparable to effects which have been reported for personalized normative feedback, which are typically in the .28 range (e.g., Dotson et al., 2015). Based on the proposed sample size of 600, given four assessment points, we anticipate the ability to detect effects of intervention contrasts and moderation effects across the small to medium range.

Considering maximum anticipated attrition rates of 15% (N=510) we will have .70, .80, and .90 power to detect effects sizes of delta = .24, .27, and .32, respectively.

14. Provide the study stopping rules part of the study protocol. Generally, stopping rules reflect one of the following conditions: 1) there is clear evidence of harm; 2) there is no likelihood of demonstrating treatment benefit (futility); 3) there is overwhelming evidence of the benefit of treatment.

There are no study stopping rules associated with the current protocol. Based on prior research, there is no reason to believe that the interventions used in this study could cause harm. Therefore, we do not plan interim analyses prior to achieving our full sample. We anticipate that the full sample will be needed to have sufficient power to detect significant group differences.

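### Section 10.1 claims the trial can detect small-to-medium moderation effects without a calculation; its own figures imply a detectable between-site difference of about .54, and the power statement gives no alpha, sidedness or link to the Aim 1 correction

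*Combined protocol and SAP*

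**What the plan says.** Section 10.1 describes the basis of the calculation as follows: "Sample size estimates were obtained for intervention contrasts". It refers to power equations for multi-level models in a named software package, and anticipates intervention effects relative to control of around .28. For the full sample of 600 with four assessments it then says "we anticipate the ability to detect effects of intervention contrasts and moderation effects across the small to medium range". The next sentence gives the only power figures: "Considering maximum anticipated attrition rates of 15% (N=510) we will have .70, .80, and .90 power to detect effects sizes of"; the three values listed there run from .24 through .27 up to .32. Appendix E item 13 repeats them: "we will have .70, .80, and .90 power to detect effects sizes of delta = .24, .27, and .32, respectively". Neither place gives alpha, sidedness, variance components or an effect size for moderation.

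Section 10.2 adds, for Aim 1: "We will utilize a Bonferroni correction with Šídák adjustment for correlated outcomes to reduce alpha inflation associated with multiple outcomes". It names eight outcomes but gives no formula, correlation or adjusted alpha.

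Site is a planned moderator. Section 6.1 sets the split at "300 from Brown University, and 300 from the University of Houston". Aim 4a in Section 4 predicts that the CAA effect will be enhanced by stronger drinker identity, "greater need for consistency, and will not differ by study site". Aim 4b predicts a stronger PNF response at Houston. Section 5 says: "If site does not moderate efficacy, then the replication of the effects of CAA across sites will provide evidence of generalizability of observed effects".

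**The concern.** A test of whether an intervention effect differs between two halves of a sample is much less precise than the test of the effect itself. A power statement derived for the main contrast does not carry over to moderation by site, and the plan shows nothing else to support that claim. This matters because Aim 4a predicts no site difference. With an imprecise test, a non-significant interaction is likely whether or not the effects are equal, and it could be read as confirmation and as part of the case for generalizability. Aim 4b, which predicts a positive site difference for PNF, meets the same limit from the other side.

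The second, smaller issue is that readers will take .80 power at .27 as a property of the Aim 1 tests. Those tests run at a corrected alpha, and the documents do not let anyone check whether the stated power does too. If it does not, a null Aim 1 result could be over-read.

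**Working it through.** **Inputs.** N=600 in three equal arms, 300 per site (Section 6.1). N=510 after 15% attrition, or 170 per arm if attrition is equal; power .70/.80/.90 at delta .24/.27/.32 (Section 10.1). Eight Aim 1 outcomes (Section 10.2). Assumed here, because the documents do not say: familywise alpha .05; for site, an equal split and common variance. z denotes the normal critical value.

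**1. Reproducing the stated pairs.** Power = Phi(delta/SE − z).
- One-sided .05 with 170 per arm: SE = sqrt(2/170) = .1085. Phi(delta/.1085 − 1.645) = .715, .801, .904.
- Two-sided .05 with SE left free to stand for a repeated-measures gain: SE from .0972 to .0982 fits all three pairs when deltas are rounded to ±.005. With SE .0975, Phi(delta/.0975 − 1.960) = .692, .791, .907.

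Both match an uncorrected .05. The one-sided match ignores the repeated measures, and the two-sided match needs an SE that the plan does not state, so neither identifies the alpha used.

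**2. Could the pairs already be corrected?** Šídák for eight independent outcomes: 1 − .95^(1/8) = .0064. Allowing ±.005 on both deltas and powers, the smallest SE permitted by the .32 pair exceeds the largest permitted by the .24 pair: .0829 against .0817 one-sided, .0780 against .0757 two-sided. So .0064 does not fit under conventional rounding. A level relaxed for correlation can fit: with the same rounding, two-sided alpha down to about .022 or one-sided down to about .011. Under one assumed form, alpha = 1 − .95^(1/8^(1−r)), these correspond to a mean correlation r of about .60 and .26.

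**3. Aim 1 power at .0064, if the pairs are uncorrected.**

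| Reading | .24 | .27 | .32 | Delta for .80 power |
|---|---|---|---|---|
| Two-sided, SE .0975, z 2.727 | .40 | .52 | .71 | .0975 × (2.727 + .842) = .348 |
| One-sided, SE .1085, z 2.490 | .39 | .50 | .68 | .1085 × (2.490 + .842) = .361 |

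**4. Site.** With variance V for the overall contrast, each site's contrast has variance 2V, and the difference between two independent sites has 4V. Its SE is 2 × SE(main), so every detectable effect doubles at the same alpha.
- N=510: 2 × .27 = .54. Directly: 2 × .0975 × (1.960 + .842) = .546 two-sided; 2 × .1085 × (1.645 + .842) = .539 one-sided.
- N=600: .54 × sqrt(510/600) = .498, about .50.
- If the pairs already carry the smallest relaxed alpha that fits (SE .0875) and site is tested at .05, N=510: 2 × .0875 × 2.487 = .435 one-sided; 2 × .0875 × 2.802 = .490 two-sided.

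Power for a site difference D, if the pairs are uncorrected, is Phi(D/(2 × SE) − z), with SE multiplied by .922 for N=600:

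| D | N=510, two-sided / one-sided | N=600, two-sided / one-sided |
|---|---|---|
| .20 | .18 / .23 | .20 / .26 |
| .30 | .34 / .40 | .39 / .44 |
| .50 | .73 / .75 | .79 / .80 |

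The 95% interval for the site difference at N=510 has half-width 1.96 × 2 × SE: .34, .38 and .43 for SE .0875, .0975 and .1085.

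**The case against.** The strongest reply on Aim 1 is that no error has been shown. That stands. A reader might infer that the power figures are wrong, or that Aim 1 is underpowered. The documents support neither: the pairs reproduce at .05, and Section 10.2 speaks of correlated outcomes, so a relaxed alpha may already be built in. If it is, no power is lost and only the reporting gap remains. Even the exclusion of .0064 depends on rounding: with deltas loosened to ±.0075 the one-sided level fits, and at ±.01 the two-sided level fits as well.

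On moderation, the claim in Section 10.1 is tied to N=600, not to the N=510 behind .27; hence the .50 given alongside .54. The plan puts no numbers on small to medium, so .54 does not by itself contradict the phrase, and a site difference of .50 would be found with power of about .73 to .80. Nor does any section anticipate a particular site difference: .28 is an expected effect against control and is not a benchmark for site. What survives is that the lower part of the range is not covered for site, and that nothing was calculated.

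A reader might also infer that Section 5 rests generalizability on a null interaction alone. It does not; it also requires replication of the CAA effect across sites. Low interaction power makes the first condition easy to meet but leaves the second in place.

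**Conclusion.** The concern holds for site. The stated ability to detect moderation across the small to medium range has no calculation behind it, and the plan's own figures imply a detectable between-site difference of about .54 at N=510, or about .50 at N=600, at the alpha used in Section 10.1. The most favourable reading that fits gives about .44 to .49 at N=510. If the pairs are uncorrected, a site difference of .30 would be detected with power of only about .34 to .44, so small and most small-to-medium differences would usually be missed. This rests on an equal site split and common variance; the doubling itself does not depend on alpha or on any repeated-measures gain.

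It would be too strong to say that the moderation claim fails for every moderator. The doubling follows from splitting the sample by site, and says nothing against drinker identity or preference for consistency; for those the claim is unsupported, not disproved.

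The Aim 1 point is a reporting gap with a conditional cost. Only if the pairs are uncorrected, with familywise .05 and the independence Šídák level, does power at .27 fall to about .50 to .52 and the effect detectable with .80 power rise to about .35 to .36.

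**What to change.** 1. In Section 10.1, remove the moderation claim for site, or replace it with: *The study was not sized for moderation; the between-site difference detectable with 80% power is about twice the main-effect value (about .54 at N=510).*
2. In Section 5 and Aim 4a, add: *A non-significant site interaction alone will not be taken as evidence of equal effects; site-specific CAA effects and their difference will be reported with 95% confidence intervals.*
3. In Section 10.1 and Appendix E item 13, state alpha and sidedness and say whether the figures are before or after the Section 10.2 correction. If they are uncorrected, restate Aim 1 power at the adjusted per-test alpha, with the adjustment formula and any assumed correlation. If they already use that alpha, saying so is enough.

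The conditional Aim 1 figures above show the possible size of the gap; they are not replacement text. The cost is one check or rerun of the power calculation and a few sentences. The stated figures may become less favourable. Sample size and data collection do not change.

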7.3.2 Screening for remote baseline sessions (Houston site)

No changes were made to the screening process at the University of Houston, as the majority of students commuted to campus prior to the pandemic.

7.4. Scheduling participants. Participants who meet screening criteria will be invited to schedule an individual in-person session using an online scheduling module (See Appendix A, Recruitment Materials, for details). The scheduling module will direct participants to select a date and time for their session and ask participants to provide their name, phone number and email address for further research study communications. A staff member will call, text, and/or email to confirm the appointment when it is made and will remind students of their appointment time and date one or two days before the scheduled appointment. At the in-person session, participants will provide written informed consent and complete the online baseline assessment

in a private room. Assignment to condition will take place after their baseline assessment; students will be stratified across conditions based on gender, a practice that has ensured baseline equivalence in drinking across conditions in several prior studies of college drinkers.

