cases). Assuming outcomes follow a negative binomial distribution with a natural log link, the following model will be the basis for evaluating intervention effects as specified in Aim 1 hypotheses:

$$\text{Level 1: } \log(E[\text{DV}]_{ti}) = \pi_{0i} + \pi_{1i}(\text{Time})_{ti} + \varepsilon_{ti} \quad \varepsilon_{ti} \sim N(0, I\sigma^2_\varepsilon)$$

$$\begin{aligned} \text{Level 2: } \pi_{0i} &= \beta_{00} + \beta_{01}(\text{site})_i + \beta_{02}(\text{CAA})_i + \beta_{03}(\text{PNF})_i + \beta_{10} + r_{00i} \\ \pi_{1i} &= \beta_{10} + \beta_{11}(\text{site})_i + \beta_{12}(\text{CAA})_i + \beta_{13}(\text{PNF})_i + r_{10i} \end{aligned}$$

where t indexes repeated-measures and i indexes participants. Campus represents the differences between Brown and UH, CAA represents the difference between CAA and the Control group, and PNF represents the difference between PNF and the control group. DV_{ti} represents the outcome vector for each individual at each assessment point. Time_{ti} measures weeks since baseline. Hypotheses associated with Aim 2 will test the relative efficacy of CAA vs. PNF using a non-inferiority design. Following the procedures outlined by Schumi & Wittes (2011), we have consulted a recent metaanalysis to obtain an effect size estimate of PNF efficacy (vs. Control) on drinking quantity ($d = .289$, 95% CI [0.117, 0.451]) and consequences ($d = .157$, 95% CI[0.037, 0.278]) (Dotson, Dunn, & Bowers, 2015). Next, we use the lower bound of each confidence interval as the basis for deriving our margin with respect to declaring non-inferiority. Thus $M1 = 0.117$ for quantity and $M1 = .037$ for consequences; these represent the most conservative estimate of the PNF effect. Then we select a smaller margin (M2) that represents the largest acceptable loss of effect when CAA is compared to PNF. Using a conservative estimate of M2 (50% of M1; USFDA, 2016), we establish non-inferiority if we retain at least half of the effect of PNF. Thus, if the lower bound confidence interval for the effect of CAA vs PNF is larger than half the lower bound estimate of the effects on drinking quantity (.117/2 = .0585) and consequences (.037/2 = .0185), we will be able to declare CAA is non-inferior to PNF.

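### The Aim 1 model estimates arm differences at baseline that randomisation sets to zero in expectation, so Time x CAA is valid but less efficient than it need be

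*Combined protocol and SAP*

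**What the plan says.** Section 10.2 sets up a two-level model for Aim 1. Each participant contributes up to four responses: baseline and the 1-, 3- and 6-month assessments. Time "measures weeks since baseline", so it is zero at baseline.

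The Level 2 equation for the intercept contains site, CAA (β02) and PNF (β03). The equation for the slope contains site, CAA (β12) and PNF (β13), plus a random slope. The plan explains that "CAA represents the difference between CAA and the Control group, and PNF represents the difference between PNF and the control group". The test is the interaction: "Time X CAA outcomes will provide direct tests of differences in change between CAA and control groups".

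No constraint is placed on β02 or β03, and Aim 1 has no baseline covariate. Only the Aim 3 mediation paths are said to control for baseline. Section 7.4 states: "Assignment to condition will take place after their baseline assessment".

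**The concern.** With time zero at baseline, β02 and β03 are differences between arms before any intervention. Under randomisation their true values are zero in expectation. Estimating them freely turns Time x CAA into a comparison of within-person change: a chance imbalance at baseline is subtracted in full instead of in proportion to how well baseline predicts follow-up.

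The cost is a larger standard error from the same data. It is present even if the effect grows exactly as the linear model assumes. It comes on top of the correction that Section 10.2 applies across eight Aim 1 outcomes.

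**Working it through.** **Inputs from the documents.** Section 10.1: 15% attrition, N=510, so 510/3 = 170 per arm; power .70, .80 and .90 at δ = .24, .27 and .32. Section 10.2: visits at months 0, 1, 3 and 6, linear time.

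**Assumptions, because the documents are silent.** Compound symmetry with correlation ρ from .3 to .8; outcome SD 1; δ = .27 is the 6-month difference, reached linearly; two-sided 5%. The plan states "Assuming outcomes follow a negative binomial distribution with a natural log link"; a Gaussian approximation is used here, so the size of the loss may differ under the planned model.

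**The plan's own power figures.** A two-sample comparison with 170 per arm gives .600/.702/.839 at two-sided 5%, which does not match. One-sided 5% gives .715/.801/.904, which is close. The planned slope test at two-sided 5% gives .703/.800/.913 if ρ is about .54, also close. The route actually used cannot be identified.

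**Formulas.** For t = 0, 1, 3, 6: Σt = 10 and Σt² = 46.

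- Free intercepts: slope-difference variance = 2(1−ρ)/(n·21), where 21 = 46 − 10²/4.
- Common baseline mean: slope-difference variance = 2(1−ρ)/(n·K), where K = 46 − 100ρ/(1+3ρ).
- SE at 6 months = 6 × the square root of the variance. Power = Φ(.27/SE − 1.96).

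At ρ = .5, K = 46 − 50/2.5 = 26. The SEs are 6√(1/3570) = .1004 and 6√(1/4420) = .0902. The variance ratio is 21/26 = .808, a 19% reduction. Equivalently, the free model needs 26/21 = 1.24 times the participants. A three-arm generalised least squares calculation gave the same SEs.

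| ρ | K | SE free | SE common | Power free | Power common | Gain (points) |
|---|---|---|---|---|---|---|
| .3 | 30.21 | .1188 | .0991 | 62.3% | 77.8% | 15.5 |
| .5 | 26.00 | .1004 | .0902 | 76.7% | 84.9% | 8.2 |
| .54 | 25.39 | .0963 | .0876 | 80.0% | 86.9% | 6.9 |
| .6 | 24.57 | .0898 | .0830 | 85.2% | 90.2% | 5.0 |
| .7 | 23.42 | .0778 | .0737 | 93.5% | 95.6% | 2.1 |
| .8 | 22.47 | .0635 | .0614 | 98.9% | 99.3% | 0.4 |

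**Random slope.** A slope variance s per month squared adds 2s/170 to both variances. At ρ = .5, power goes from 68.6% to 76.0% with s = .005 and from 61.7% to 68.0% with s = .01: gains of 7.4 and 6.3 points.

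**Risk of the constraint.** If the arms truly differed at baseline by 0.10 SD throughout, the free-intercept slope would be unaffected. The constrained 6-month effect would shift by 6 × 0.10 × [10/(1+3ρ)] / [K/(1−ρ)]. At ρ = .5 this is 6 × 0.10 × 4/52 = 0.046 SD; at ρ = .3 it is 0.073 SD.

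**Follow-ups only.** With baseline as a covariate but free arm main effects kept beside Time x CAA, only months 1, 3 and 6 inform the slope. The sum of squares is 46 − 100/3 = 12.67. At ρ = .5 the SE is 6√(1/(170 × 12.67)) = .129 and power is about 55%, below the planned model's 76.7%.

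**The case against.** The strongest objection is that the free intercept protects against something the constraint does not. Section 7.4 places assignment after the baseline assessment, but in the Appendix C remote session script an identifier that depends on condition is selected before the participant answers the questionnaires, with the research assistant still on the call. Remote sessions began in March 2020 at Brown and April 2020 at Houston, and were Brown's only format from Fall 2020. A reader might infer that baseline is contaminated and the constraint invalid. The documents do not support that: randomisation still equalises the true baseline means unless knowledge of condition changes the answers. What stands is that the passages conflict and that a sensitivity analysis is needed.

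Second, the constraint does not clearly suit all eight outcomes. Section 9.1.4 describes dissonance as felt right after the CAA activity, and Section 5 places attitudes and dissonance at posttest. Yet both sit under the baseline assessment in Section 9.1, and Section 9.2 says follow-up measures match baseline. If a session value is taken after the activity, the arms are meant to differ and the constraint would be wrong. This stands.

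Third, the plan openly targets change, its test is sound, and the size of the gain is unknown. This also stands, but it limits the size of the point and does not remove it.

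**Conclusion.** The point holds as one of efficiency. The planned test is valid and unbiased, but it spends information on two quantities that randomisation already fixes in expectation. The gain from a common baseline mean runs from about 15 points at ρ = .3 to under 1 at ρ = .8, and is about 7 to 8 at ρ of .5 to .54, under the assumptions listed above.

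Three stronger readings are tempting and not supported:

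- That the plan loses 8 points as such. That figure needs ρ = .5, and the documents give no correlation.
- That the stated .80 would become about .88. Nothing shows that .80 is the power of this slope test; a one-sided two-sample test fits about as well.
- That Aim 2 necessarily suffers the same loss. Section 10.2 gives that contrast in effect-size units and does not say that it is β12 − β13.

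**What to change.** - For outcomes measured before the intervention activity, set β02 = β03 = 0 in the intercept equation, keep site, and keep β12 and β13 as the effects. Use the same model for the CAA–PNF contrast if it is taken from this model.
- State when dissonance is measured in the session. Do not constrain any outcome whose session value follows the activity.
- If follow-ups only are modelled with baseline as a covariate, do not test Time x CAA beside free arm main effects. Test the arm effect directly, or force it through zero at baseline.
- Reconcile Section 7.4 with the remote script on when condition is assigned and known, and report the free-intercept model as a sensitivity analysis.
- State the assumed correlation, alpha and sidedness.

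The cost is two terms dropped from one equation, one added sensitivity analysis and some clarifying text; no extra participants or visits. The price is exposure to a true baseline difference, about 0.05 SD in the 6-month effect per 0.10 SD at ρ = .5. The benefit is small if repeated measures correlate at about .7 or above.
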